4.10. Analysis Populations

Intent-to-Treat (ITT): Includes all enrolled/randomized subjects. All randomized subjects will be included in the ITT analysis, where the arm classification is based on the randomized arm, even if they never receive it or receive treatment with another procedure. If the final analysis is only on the enriched population (refer to adaptive design plan in Appendix F of study protocol) then only those subjects in the enriched group will be included in the final analysis, based in ITT. This population is the primary population for all efficacy parameters.

As-Treated Analysis (AT): The same as the ITT population except subjects are analyzed based upon actual treatment received. Subjects who receive only medical therapy are included in the control arm, and subjects who receive any device-based therapy are included in the Trevo arm.

Per-Protocol (PP): A subset of the intent-to-treat population, including subjects who did not violate the inclusion/exclusion criteria or experience significant protocol deviations.

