4.13. Interim Analysis

Primary endpoint interim analyses will begin after 150 subjects have been enrolled, and subsequent interim analyses will take place after every 50 subjects.

The analysis performed at each interim analysis will include:

- Modeling of the treatment effect for each infarct size in the population,
- Longitudinal modeling to impute final outcomes for subjects for which we have 30-day mRS scores but not 90-day mRS scores, and
- Estimation of the distribution of infarct sizes.

The mathematical details and assumptions for these analyses are described in Appendix F.

The possible adaptations that may be made at the interims are to:

- Stop the trial for futility,
- Enrich the population if it appears that the device benefits one subset of the population considerably more than another, or
- Stop enrollment for expected success.

The rules for each decision/adaptation are defined below. Additional details pertaining to statistical models are given in the adaptive design plan in Appendix F of Study protocol.

4.13.1. *Interim Monitoring for Early Futility*

Interim safety analyses will be performed concurrently with the primary endpoint analyses.

The trial stops for futility if there is less than 10% predictive probability that the trial would be successful if enrolled to the maximum sample size under any enrichment possibility.

4.13.2. *Enrichment*

Enrichment decisions can occur starting at 150 subjects enrolled and the last opportunity to enrich is at 400 subjects. The candidate enriched populations that the trial considers are based on infarct sizes. The five possible subpopulations are defined by infarct size as measured using RAPID MR-DWI or CTP-rCBF maps:

1. The full population of infarct sizes 0 to 50 cc
2. Infarct sizes of 0 to 45 cc
3. Infarct sizes of 0 to 40 cc
4. Infarct sizes of 0 to 35 cc
5. Infarct sizes of 0 to 30 cc

If the population is enriched, subjects with larger infarct sizes are no longer enrolled, and the final efficacy analysis omits subjects with larger infarct sizes from consideration. Enrichment decisions are irreversible, but the trial can enrich the population further after it has already been enriched.

The design will enrich if one of the following conditions is met:

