4.15.5. Analysis of Secondary Effectiveness Endpoints

The analysis population to prove the efficacy of the Trevo® Retriever consists of two arms: Treatment arm and Control arm. The two arms are defined as below.

- a. Treatment arm: the subjects who are randomized to the Trevo thrombectomy plus medical management.
- b. Control arm: the subjects who are randomized to the medical management alone.

The following Secondary Effectiveness Endpoints will be analyzed:

Both Arms:

Stryker Neurovascular

Document Title: DAWN™ Trial Statistical Analysis Plan

Document Number: CDM10000704

Rev: AB

- Proportion of subjects with “early response” at Day 5-7/Discharge (whichever is earlier), defined as a NIHSS drop of ≥ 10 points from baseline or NIHSS score 0 or 1 will be presented by providing the count and percentage for each treatment arm. The difference in the percentage between two arms and the 95% CI for the difference will be calculated using the normal approximation to binomial. P-values will be calculated by the Chi-squared test or Fisher’s exact test as appropriate. Relative Risk (RR) was provided as Trevo thrombectomy plus medical management / medical management.
- Difference in all-cause mortality rates between the two arms and the 95% CI for the difference will be calculated using the normal approximation to binomial. P-values will be calculated by the Chi-squared test or Fisher’s exact test as appropriate. Relative Risk (RR) was provided as Trevo thrombectomy plus medical management / medical management.
- Difference in median final infarct size at 24 (-6/+24) hours from randomization, by MRI T2/Flair or CT (if contraindicated for MR) will be presented with n, mean, median, interquartile, standard deviation, minimum, and maximum between two treatment arms. P-values will be calculated with t-test assuming un-equal variances to compare the difference between two treatment arms.
- Difference in revascularization rates at 24 (-6/+24) hours from randomization, by CT-MR core lab assessment of vessel patency on CTA/MRA between the two arms and the 95% CI for the difference will be calculated using the normal approximation to binomial. P-values will be calculated by the Chi-squared test or Fisher’s exact test as appropriate. Relative Risk (RR) was provided as Trevo thrombectomy plus medical management / medical management.

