STRYKER CONFIDENTIAL - THIS DOCUMENT CONTAINS CONFIDENTIAL AND PROPRIETARY INFORMATION THAT IS THE PROPERTY OF STRYKER CORPORATION. NEITHER THIS DOCUMENT NOR THE INFORMATION HEREIN MAY BE REPRODUCED, USED, OR DISCLOSED TO ANY THIRD PARTY WITHOUT THE PRIOR WRITTEN CONSENT OF STRYKER CORPORATION

Treatment Arm Only:

Analysis of vessel reperfusion rates, by angiography measurement of modified TIC1 > 2b will be consistently reported with the count, rate and exact Clopper-Pearson 95% CI separately by post device and post procedure in treatment arm.

The enriched populations will be employed for secondary effectiveness endpoints analysis (refer to adaptive design plan in Appendix F of study protocol).

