5.3. Analysis of Primary Safety Endpoints

Both Arms:

Incidence of stroke-related mortality at 90 days will be presented by providing the count and percentage for each treatment arm. The difference in the percentage between two arms and the 95% CI for the difference will be calculated using the normal approximation to binomial. P-values will be calculated by the Chi-squared test or Fisher's exact test as appropriate. Relative Risk (RR) was provided as Trevo thrombectomy plus medical management / medical management.

ITT population will be used for the analysis of Primary Safety Outcome.

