6.3. Rules for Calculating Rates and Handling Denominators

For Safety events, binary rates will be calculated using as a denominator as the number of all Subjects in the study, regardless of their follow-up time.

Stryker Neurovascular

Document Title: DAWN™ Trial Statistical Analysis Plan

Document Number: CDM10000704

Rev: AB

Other binary rates such as mRS or NIHSS will be calculated using a denominator as the total number of the available data for the outcome, excluding missing values.

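### If the trial enriches, the SAP compares all-cause mortality only in the enriched population, against Protocol section 4 and with no planned comparison in all randomised subjects

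*SAP*

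**What the plan says.** SAP 4.15.5 lists, among the secondary effectiveness endpoints for both arms, the "Difference in all-cause mortality rates between the two arms and the 95% CI for the difference". It gives no time point. The section ends with a rule for the whole list: "The enriched populations will be employed for secondary effectiveness endpoints analysis". It refers to Appendix F of the protocol for details.

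SAP 4.13.2 says what enrichment does to subjects already in the trial: "the final efficacy analysis omits subjects with larger infarct sizes from consideration".

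Other places that set a population for mortality or safety:

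- SAP 5.3, for stroke-related mortality at 90 days: "ITT population will be used for the analysis of Primary Safety Outcome".
- SAP 4.10 opens the ITT definition with "Includes all enrolled/randomized subjects". It then adds that if the final analysis is restricted by enrichment, "then only those subjects in the enriched group will be included in the final analysis, based in ITT". Protocol 8.5 has a similar clause.
- SAP 6.3, for safety events: "binary rates will be calculated using as a denominator as the number of all Subjects in the study".
- Protocol section 4, in its opening paragraph, has the clinical endpoints and safety outcomes evaluated in everyone randomised, whether or not the assigned treatment was delivered. Protocol 4.2 then lists all-cause mortality as one of those endpoints.

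**The concern.** A subject randomised with a larger infarct contributes follow-up and, possibly, a death. If that infarct band is later closed, SAP 4.15.5 removes the subject from the all-cause mortality comparison. The removal depends on interim outcomes, so the comparison is no longer protected by randomisation in the way that an all-randomised comparison is. If treated subjects in the closed band died more often, the reported difference would look better for the device than the trial's full experience.

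Restricting efficacy after enrichment is reasonable, because the efficacy claim is then made for the smaller population. Mortality serves a second purpose: it records what happened to everyone exposed to randomisation. The SAP raises the success threshold to allow for enrichment (SAP 4.14), but nothing comparable applies to the mortality comparison.

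**Working it through.** The documents attach no figure to this point, so there is none to reproduce. The check is a comparison of texts, followed by an illustration of size.

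**1. Populations side by side, if enrichment occurs**

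| Place | Outcome | Population |
|---|---|---|
| Protocol section 4 | Endpoints and safety outcomes | All randomised |
| SAP 4.15.5 | All-cause mortality | Enriched |
| SAP 5.3 with 4.10 | Stroke-related mortality | ITT: all randomised, or the enriched group if the enrichment clause applies |
| SAP 6.3 | Safety events | All subjects in the study |

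No place in the SAP specifies a between-arm comparison of all-cause mortality in all randomised subjects.

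**2. How subjects leave the comparison.** SAP 4.13 gives two enrichment rules. The first closes the highest open 5 cc band when its posterior probability of benefit is under 40%. The second moves to a smaller population when that raises the predictive probability of success by at least 10%. Both use interim mRS data. Death scores 0 on the weighted mRS (protocol synopsis), so excess treated-arm deaths can help to close a band. But mRS 5 also scores 0, so the weighted score does not separate death from the most severe disability.

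**3. Number omitted.** Inputs: enrichment is possible from 150 to 400 subjects (SAP 4.13.2), and the proportion at mRS 6 in the simulated control arm is 0.19 (Protocol Table 6). The share dropped is an assumption, 10-30%, because the documents give no infarct-size distribution. One mortality rate is applied to both arms.

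Subjects omitted = share × number enrolled at the look. Deaths omitted = subjects omitted × 0.19.

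| Enrichment at | Subjects omitted | Deaths omitted |
|---|---|---|
| 150 | 0.10 × 150 = 15 to 0.30 × 150 = 45 | 2.9 to 8.6 |
| 400 | 0.10 × 400 = 40 to 0.30 × 400 = 120 | 7.6 to 22.8 |
| Never | 0 | 0 |

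These are totals over both arms. At a common rate they imply no between-arm distortion.

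**4. What a distortion would need.** Suppose 500 are randomised (250 per arm), enrichment occurs at 400, 20-30% of those are dropped (80-120, or 40-60 per arm), and mortality is 19% in both retained arms and in the dropped controls. Let treated-arm mortality in the dropped subjects be 30-40%, a hypothetical range. The enriched risk difference is 0. The all-randomised difference is (excess × dropped per arm) / 250:

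- Low end: 0.11 × 40 / 250 = 0.0176, or +1.8 percentage points.
- High end: 0.21 × 60 / 250 = 0.0504, or +5.0 percentage points.

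The 95% CI half-width is about 7 points. Deaths omitted run from 40 × (0.19 + 0.30) = 19.6 to 60 × (0.19 + 0.40) = 35.4.

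**5. The two mortality tables.** If ITT in SAP 5.3 means all randomised, stroke-related deaths are counted in retained and dropped subjects, and all-cause deaths in retained subjects only. Reported stroke-related deaths exceed reported all-cause deaths whenever stroke-related deaths among the dropped outnumber non-stroke deaths among the retained. If ITT follows the enrichment clause, the denominators agree, but both tables omit the dropped subjects.

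**The case against.** The strongest reply is that this is a pre-specified and coherent choice. All-cause mortality is listed as an effectiveness endpoint in both documents, and it is matched to the population of the primary analysis. Appendix F, to which SAP 4.15.5 refers, is not included in these documents and might say more. This explains the choice but does not remove the conflict with Protocol section 4. Protocol 8.7, moreover, names only the weighted and dichotomous analyses when it restricts the final analysis to the enriched population.

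A reader might infer that the deaths vanish from the report. The documents do not support that. A fatal event is an SAE, and SAP 5.2 summarises SAEs by arm for all randomised subjects. The CEC adjudicates all deaths, and the DMC reviews mortality in both arms. SAP 4.15.2 tabulates mRS by arm, with death as category 6, although it names no population. What is missing is a planned all-cause comparison. Under SAP 5.1, death is recorded only as the outcome of another event, so the adverse event tables do not supply one.

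A reader might also infer a proven bias toward the device. That is not shown. Neither enrichment rule acts on mortality as such, and the second can drop a band whose effect is merely smaller. Even the hypothetical +1.8 to +5.0 points lie within the confidence interval half-width.

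Finally, a reader might take it as settled that stroke-related mortality uses everyone randomised, and that the two tables could not be reconciled. The enrichment clause in SAP 4.10 leaves the first open, though all randomised is the better reading: the clause concerns the final efficacy analysis, SAP 4.15.5 and 5.3 name different populations, and SAP 6.3 uses all subjects. The second goes too far, because counts and percentages by arm (SAP 4.3) would show the differing denominators.

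**Conclusion.** The point holds, on condition that enrichment occurs. SAP 4.15.5 then limits the all-cause mortality comparison to a population selected on interim outcomes. That conflicts with Protocol section 4, sits uneasily with SAP 6.3, and leaves the relation to SAP 5.3 dependent on an ambiguous ITT definition. Bias toward the device is plausible, but its direction and size are not established. Non-stroke deaths in dropped subjects would enter no planned between-arm mortality comparison.

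The omission is about 3-9 deaths for enrichment at 150 and 8-23 at 400. These figures rest on the assumed 10-30% share and on 19% mortality in both arms; they measure how much information is left out, not how large a bias is. The change should be made because the plan allows enrichment and must cover that branch. It is not a threat to the primary analysis: type I error, power, sample size and the 0.986 threshold are unaffected.

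**What to change.** In SAP 4.15.5, except all-cause mortality from the enriched-population rule: analyse 90-day all-cause mortality in all randomised subjects by assigned arm, regardless of enrichment, and report the enriched-population result as supportive. Naming 90 days also supplies the missing time point and matches the primary safety outcome.

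In SAP 4.10 or 5.3, state that for mortality and safety outcomes ITT means all randomised subjects regardless of enrichment. A cross-reference to the population used in SAP 5.3 would not be enough, because that population is itself ambiguous.

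The cost is two SAP sentences and one extra table. No new data are needed, since follow-up through 90 days is planned for every enrolled subject. SAP section 1 allows revision before final data lock.

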4.15.6. Pooling Across Sites

Results for the primary efficacy endpoint will be presented by sites and treatment arms. Poolability across sites will be assessed using Proc GLM in SAS to fit an ANCOVA model on the weighted mRS with terms for treatment arm, site, and the interaction of treatment arm and site. A p-value less than 0.10 for the interaction term will be taken as evidence that there are significant differences in treatment effect between sites. If the effect is found to vary by site, then the effect will be analyzed using Proc Mixed in SAS using a hierarchical model with random site effect. Sites with fewer than 10 Subjects will be combined and treated as one site in examining the pooling.

4.15.7. Other Pre-planned Analyses

Both Arms:

Incidence of symptomatic ICH (per the SITS MOST definition) will be presented by providing the count and percentage for each treatment arm. The difference in the percentage between two arms and the 95% CI for the difference will be calculated using the normal approximation to binomial. P-values will be calculated by the Chi-squared test or Fisher's exact test as appropriate. Relative Risk (RR) was provided as Trevo thrombectomy plus medical management / medical management.

Treatment Arm only:

Summary of functional independence (mRS 0-2) by reperfusion status, will be provided by N, percentage and exact Clopper-Pearson 95% CI, separately by post-device and post-procedure in treatment arm.

Document Title: DAWN™ Trial Statistical Analysis Plan

Document Number: CDM10000704

Rev: AB

4.15.8. Health Economic Evaluation

The health economic evaluation will not be part of this SAP. However, the analyses to compare overall health care costs and resource utilization between mechanical intervention and standard medical care may be needed in the future.

STRYKER CONFIDENTIAL - THIS DOCUMENT CONTAINS CONFIDENTIAL AND PROPRIETARY INFORMATION THAT IS THE PROPERTY OF STRYKER CORPORATION. NEITHER THIS DOCUMENT NOR THE INFORMATION HEREIN MAY BE REPRODUCED, USED, OR DISCLOSED TO ANY THIRD PARTY WITHOUT THE PRIOR WRITTEN CONSENT OF STRYKER CORPORATION

Stryker Neurovascular

Document Title: DAWN™ Trial Statistical Analysis Plan

Document Number: CDM10000704

Rev: AB

5. SAFETY ANALYSIS

5.1. Adverse Events

TABLE 3. ADVERSE EVENT DEFINITIONS AND CLASSIFICATION

Term	Definition	Reference
Adverse Event (AE)	Any untoward medical occurrence in a subject. This definition does not imply that there is a relationship between the adverse event and the device under investigation.	ISO 14155-1
Adverse Device Effect (ADE)	Any untoward and unintended response to a medical device. Note 1: This definition includes any event resulting from insufficiencies or inadequacies in the instructions for use or the deployment of the device. Note 2: This definition includes any event that is a result of a user error.	ISO 14155-1
Serious adverse event (SAE)	An adverse event that: 
 • led to death • resulted in a life-threatening illness or injury • resulted in a permanent impairment of a body structure or a body function • required in Subject hospitalization or prolongation of existing hospitalization • resulted in medical or surgical intervention to prevent permanent impairment to body structure or a body function • led to fetal distress, fetal death or a congenital abnormality or birth defect 	ISO 14155-1
Serious Adverse Device Effect (SADE)	An adverse device effect that has resulted in any of the consequences characteristic of a serious adverse event or that might have led to any of these consequences if suitable action had not been taken or if circumstances had been less fortunate.	ISO 14155-1
Unanticipated Adverse Device Effect (UADE)	Any serious adverse effect on health or safety or any life-threatening problem or death caused by, or associated with a device, if that effect, problem, or death was not previously identified in nature, severity, or degree of incidence in the investigational plan or application (including a supplementary plan or application), or any other unanticipated serious problem associated with a device that relates to the rights, safety, or welfare of subjects.	21 CFR Part 812

STRYKER CONFIDENTIAL - THIS DOCUMENT CONTAINS CONFIDENTIAL AND PROPRIETARY INFORMATION THAT IS THE PROPERTY OF STRYKER CORPORATION. NEITHER THIS DOCUMENT NOR THE INFORMATION HEREIN MAY BE REPRODUCED, USED, OR DISCLOSED TO ANY THIRD PARTY WITHOUT THE PRIOR WRITTEN CONSENT OF STRYKER CORPORATION

Stryker Neurovascular

Document Title: DAWN™ Trial Statistical Analysis Plan

Document Number: CDM10000704

Rev: AB

Underlying (pre-existing) symptoms or diseases are not reported as Adverse Events (AEs) unless there is an increase in severity or frequency during the course of the investigation. Death should not be recorded as an adverse event, but should only be reflected as an outcome to another specific AE. Any AE experienced by the study subject after enrollment (equal to the time of randomization) must be recorded in the CRF.

All AEs and SAEs will be monitored and collected from the time of enrollment (equal to the time of randomization) through 90 day follow-up visit. All SAEs and UADEs must be reported to Stryker NV within 24 hours of becoming aware of their occurrence in order to comply with Stryker NV's regulatory reporting requirements.

In subjects who are randomized to the Treatment Arm, the Investigator must assess the relationship of the adverse event to the study device using the following criteria categories and definitions:

Unrelated - The adverse event is determined to be due to a concurrent illness or effect of another device/drug and is not related to the investigational product.

Related - There is a strong relationship to investigational product, or recurs on re-challenge, and another etiology is unlikely.

Unknown – There is not enough information to make a determination.

In subjects who are randomized to the Treatment Arm, the Investigator must assess the relationship of the adverse event to the index procedure using the following categories and definitions:

Unrelated - The adverse event is determined to be due to a concurrent illness or effect of a device/drug and is not related to the index procedure.

Related - There is a strong relationship to index procedure, or recurs on re-challenge, and another etiology is unlikely.

Unknown – There is not enough information to make a determination.

5.2. Summaries of Adverse Events

All summaries of adverse events will be based on events that occurred during the study. Adverse events will be mapped to preferred terms and body systems using the Medical Dictionary for Regulatory Activities (MedDRA) coding dictionary. The number and percentage

STRYKER CONFIDENTIAL - THIS DOCUMENT CONTAINS CONFIDENTIAL AND PROPRIETARY INFORMATION THAT IS THE PROPERTY OF STRYKER CORPORATION. NEITHER THIS DOCUMENT NOR THE INFORMATION HEREIN MAY BE REPRODUCED, USED, OR DISCLOSED TO ANY THIRD PARTY WITHOUT THE PRIOR WRITTEN CONSENT OF STRYKER CORPORATION

of subjects experiencing adverse events will be summarized by system organ class and preferred term. Summaries by relationship to the study device and procedure will also be provided. Serious adverse events will be summarized separately.

Results will be presented for each of the following 3 groups

- Subjects randomized to the Treatment arm,
- Subjects randomized to the Control arm, and
- All randomized subjects.

